2.2.1 Randomization and drug dispensing irregularities

There is no randomization procedure in LTS12551. Drug-dispensing irregularities occur whenever:

• A patient is dispensed an IMP kit not allocated by the IVRS, such as, a) a patient at any time in the study is dispensed a different treatment kit than as assigned, or b) a non-screened patient is treated with IMP reserved for enrolled patients.

Drug-dispensing irregularities will be monitored throughout the study and reviewed on an ongoing basis.

All drug-dispensing irregularities will be documented in the clinical study report. If the number of irregularities is large enough to make a tabular summary useful, the irregularities will be categorized and summarized among enrolled patients (number and percentages). Non-enrolled and treated patients will be described separately.

Drug-dispensing irregularities to be prospectively identified include but are not limited to:
Randomization and drug allocation irregularities
Kit dispensation without IVRS transaction
Erroneous kit dispensation
Kit not available
Subject enrolled twice
Subject switched to another site

2.3 ANALYSIS POPULATIONS

The primary analysis population is the safety population. All safety and efficacy analyses will be performed based on the safety population.

2.3.1 OCS dependent and Non-OCS dependent populations

The OCS dependent population is defined as the patients who participated in EFC13691 study and then subsequently enrolled in the LTS12551 study.

The non-OCS dependent population is defined as the patients who were not on daily chronic OCS therapy and participated in DRI12544, EFC13579 or PDY14192 studies and then enrolled in the LTS12551 study.

The patients from the EFC13691 study are considered as a different patient population from the patients from the DRI12544, EFC13579 or PDY14192 studies. This is because the patients from the EFC13691 study are more severe at the baseline of parent study, are using a different background controller medication, and potentially could have different safety profiles and different efficacy effect from the patients enrolled from the DRI12544, EFC13579 or PDY14192 studies. In addition, for the patients from the EFC13691 study only, LTS12551 study will assess the efficacy endpoints linked to the reduction of the OCS dose.

Furthermore, all analyses planned in LTS12551 will be performed and presented separately for the patients from the EFC13691 study and the patients from the DRI12544, EFC13579 or PDY14192 studies, except for the endpoints (see Section 2.1.3.7) that are collected for the patients from EFC13691 study only.

2.3.2 Safety population

The safety population is defined as the patients who have actually received at least 1 dose or part of a dose of the IMP in LTS12551.

Enrolled patients for whom it is unclear whether they took the IMP or not will be included in the safety population as enrolled.

The treatment category "Placebo/Dupilumab" is defined as the patients who have been in the actual placebo arms of the parent studies and exposed to Dupilumab in LTS12551. The treatment category "Dupilumab/Dupilumab" is defined as the patients who have been in the actual Dupilumab arms of the parent studies and exposed to Dupilumab in LTS12551.

For the OCS dependent patients, results of each planned analysis will be presented by "Placebo/Dupilumab", "Dupilumab/Dupilumab" and "All".

For the non-OCS dependent patients, results of each planned analysis will be presented by the parent study and "All", and further by "Placebo/Dupilumab" and "Dupilumab/Dupilumab" within each parent study.

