1 OVERVIEW AND INVESTIGATIONAL PLAN

1.1 STUDY DESIGN AND RANDOMIZATION

LTS12551 is a multinational, multicenter, 1-year (48 weeks) or 2-year (96 weeks) single arm extension study to evaluate the long-term safety and tolerability of dupilumab in patients with asthma, who completed the treatment and follow-up period in the DRI12544 study, or who completed the treatment period in the EFC13579, EFC13691 or PDY14192 studies.

In the LTS12551 study, dupilumab 300 mg is administered subcutaneously (SC) every 2 weeks (q2w), as an add-on therapy to a variety of allowable combinations between inhaled corticosteroid (ICS) and other controller medications as maintained during the parent study, including the oral corticosteroids (OCS) medication for the patients from the EFC13691 study. The LTS12551 consists of three periods:

- Screening Period (0-3 weeks, if applicable)
- Treatment Period (48 weeks open-label period for the patients enrolled after the protocol amendment 4, or 96 weeks open-label period for the patients enrolled before the protocol amendment 4)
- Post-treatment Period (12 weeks, dupilumab-free follow-up period)

The 4 parent studies are described briefly as follows:

DRI12544: A phase 2b, randomized, double-blind, placebo-controlled, dose ranging, parallel group study comparing different doses and regimens of dupilumab SC for 24 weeks in patients with moderate to severe, uncontrolled asthma. Patients were randomized in ratio of 1:1:1:1:1 into 5 arms, dupilumab 200 mg every 4 weeks (q4w), dupilumab 300 mg q4w, dupilumab 200 mg q2w, dupilumab 300 mg q2w, and placebo. Patients were allowed to administer moderate- or high-dose inhaled corticosteroid (ICS) in combination with long-acting beta agonist (LABA) as follows: mometasone furoate / formoterol, budesonide / formoterol, and fluticasone propionate / salmeterol in the treatment period, and continued with the stable dosage of controller medications in the 16-week post-treatment follow-up period. There were 776 patients enrolled in DRI12544.

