EFC13579: A phase 3, randomized, double blind, placebo-controlled, parallel group study to evaluate the efficacy and safety of dupilumab SC for 52 weeks in patients with persistent asthma. Patients were randomized in ratio of 2:2:1:1 into the following regimens, dupilumab 200 mg q2w, dupilumab 300 mg q2w, placebo matching 200mg q2w and placebo matching 300 mg q2w. In the treatment period, patients are allowed to administer a stable background therapy of medium to high dose of inhaled corticosteroid (ICS) in combination with a second controller medication (for example, long-acting beta agonist [LABA], leukotriene receptor antagonist [LTRA], theophylline, and etc.), and potentially plus a third controller medication. There were in total 1902 patients randomized for EFC13579.

EFC13691: A phase 3, randomized, double-blind, placebo-controlled study to evaluate the efficacy and safety of dupilumab 300 mg q2w SC for 24 weeks in patients with severe oral corticosteroid dependent asthma. Patients are randomized in a ratio of 1:1 to dupilumab 300 mg q2w and matching placebo, which will be given on top of standard of care and of oral corticosteroids. During the course of the study, the oral corticosteroid (OCS) [prednisone/prednisolone] doses will be adjusted to the dose required for the maintenance of asthma control. In the screening period, patients experience an OCS dose optimization process. In the treatment period, patients continue with the optimized OCS doses in the first 4 weeks, then have the OCS dose down-titrated till Week 20, and at last maintain on the Week 20 OCS dose for the rest 4 weeks. In the meantime, patients are also allowed to be on a stable dose of high dose ICS with a second controller medication (LABA, LTRA, theophylline, etc), and potentially plus a third controller medication per requested by patients. There were in total 210 patients randomized for EFC13691.

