2.4.6.1 Pharmacokinetic analysis

The PK analyses will be performed on the PK population (Section 2.3.4). Serum concentrations of dupilumab will be summarized using arithmetic and geometric means, SD, standard error of the mean (SEM), coefficient of variation (CV), minimum, median and maximum by visit. If date and/or time of the drug intake and/or sampling are missing, then the concentration will not be taken into account. For the patients from the Dupilumab arms of EFC13579, EFC13691 or PDY14192 studies,, if the pre-dose concentration values at Week 0 of LTS12551 are below the lower limit of quantitation (LLOQ = 78 ng/ml), one-half of LLOQ will be used; for the patients from the Dupilumab arms of DRI12544 study, the pre-dose concentration value at Week 0 of LTS12551 should use 0; for the patients from the Placebo arms of parent studies, the pre-dose concentration value at Week 0 of LTS12551 should use 0 of LTS12551 should use 0 of LTS12551 should use 0. Values will be expressed in the tables with no more than three significant figures.

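### In EFC13579 the Dupilumab/Dupilumab column mixes former 200 mg q2w and 300 mg q2w patients, so its mean concentration would rise about 20% to 31% after Week 0 from the dose change alone

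*SAP*

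**What the plan says.** - **Grouping.** In SAP 2.3.2 the Dupilumab/Dupilumab category "is defined as the patients who have been in the actual Dupilumab arms of the parent studies and exposed to Dupilumab in LTS12551". The same section sets the layout: "For the non-OCS dependent patients, results of each planned analysis will be presented by the parent study and" overall, then by Placebo/Dupilumab and Dupilumab/Dupilumab within each parent study.
- **Parent regimens (SAP 1.1).** For EFC13579, "Patients were randomized in ratio of 2:2:1:1 into the following regimens, dupilumab 200 mg q2w, dupilumab 300 mg q2w", with two matching placebos; "There were in total 1902 patients randomized for EFC13579". DRI12544 had five equal arms: "dupilumab 200 mg every 4 weeks (q4w), dupilumab 300 mg q4w, dupilumab 200 mg q2w, dupilumab 300 mg q2w, and placebo". EFC13691 and PDY14192 compared only 300 mg q2w with placebo.
- **Transition (SAP 1.1).** Everyone receives 300 mg q2w in LTS12551. Patients from EFC13579, EFC13691 and PDY14192 enter at the parent end-of-treatment visit, with neither a break nor a loading dose. Those from DRI12544 had been off drug for at least 16 weeks and received a 600 mg loading dose.
- **Concentrations.** SAP 2.4.6.1 states: "Serum concentrations of dupilumab will be summarized using arithmetic and geometric means", among other statistics, by visit. SAP 2.5.4 takes the EFC13579 Week 0 value from the parent end-of-treatment visit. For DRI12544, SAP 2.4.6.1 enters Week 0 as zero.
- **No split elsewhere.** Parent dose does not appear as a factor in the efficacy subgroups (2.4.4.1), the safety subgroups (2.4.5.6), or the PK, PD and ADA sections (2.4.6.1, 2.4.6.2, 2.4.7).

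**The concern.** Half of the EFC13579 dupilumab patients change dose on Day 1 of LTS12551 and half do not, and the planned column cannot tell them apart. Systemic exposure is a secondary objective (SAP 1.2.2). A by-visit mean that starts from a mixture of two dose levels and continues at one will move for a reason unrelated to how concentrations behave under continued 300 mg q2w. A reader of the table could not separate that shift from a real change over time.

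The second loss is descriptive. The EFC13579 300 mg arm is the largest group continuing the LTS12551 regimen without interruption, and it follows the longest parent treatment (52 weeks). The planned layout gives it no column of its own for PK, ADA or adverse events.

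**Working it through.** **1. The plan's own total.** SAP 1.3 gives a maximum of 2930. From SAP 1.1: 776 + 1902 + 210 + 42 = 2930, which agrees.

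**2. Composition of the EFC13579 column.** With 2:2:1:1 allocation of 1902 patients, each dupilumab arm has 1902 × 2/6 = 634. The column holds up to 634 + 634 = 1268, half of them from 200 mg q2w. These are ceilings that assume full rollover. The 50:50 share needs only equal rollover in the two arms.

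**3. Patients on unbroken 300 mg q2w.** EFC13579: 634. EFC13691: 210/2 = 105. PDY14192: 42/2 = 21. Total 634 + 105 + 21 = 760. The planned columns isolate 105 + 21 = 126 of them (126/760 = 17%). The other 634 (83%) sit in the mixed column. DRI12544 patients are not counted, because all of them were interrupted.

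**4. Relative concentration at 200 mg.** The documents give no concentrations by dose, so this is an assumption with a range. Protocol 4.2 puts mean steady-state exposure at 300 mg q2w 2 to 3 times below that at 300 mg weekly. Doubling the dose rate therefore multiplies exposure by 2 to 3. If exposure varies as dose rate to the power b, then b = log2(2) = 1 to log2(3) = 1.585. With 300 mg q2w set to 1, the 200 mg q2w level is (2/3)^b:

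- b = 1 (dose-proportional): 0.667
- b = 1.585: 0.526

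**5. Apparent rise in the pooled column.** Week 0 mean = 0.5 × (2/3)^b + 0.5 × 1. Rise to the 300 mg level = 1/(Week 0 mean) − 1. Geometric rise = (1/(2/3)^b)^0.5 − 1.

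| | b = 1 | b = 1.585 |
|---|---|---|
| Week 0 arithmetic mean | 0.833 | 0.763 |
| Arithmetic rise | 20% | 31% |
| Geometric rise | 22% | 38% |
| Rise in former 200 mg patients | 50% | 90% |
| Rise in former 300 mg patients | 0% | 0% |

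If unequal rollover made the 200 mg share 40% to 60%, the arithmetic rise would run from 15% (40%, b = 1) to 40% (60%, b = 1.585).

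**6. Where the effect stops.** EFC13691 and PDY14192 have no 200 mg arm, so nothing is mixed. DRI12544 dupilumab patients start from a Week 0 value of zero after washout, so their rise is re-initiation. In the non-OCS All column, placebo and DRI12544 patients also start at zero. There the 200 to 300 mg change explains only about 13% to 17% of the rise: 634 × (1 − (2/3)^b)/2720, divided by 1 − (634 × (2/3)^b + 634 + 21)/2720, where 2720 = 776 + 1902 + 42.

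**The case against.** The study is single-arm and descriptive, with no confirmatory efficacy analysis and no systematic safety testing. The treatment-emergent period starts with the first LTS12551 dose, from which point everyone is on 300 mg q2w, so the primary endpoint is computed correctly under the pooled layout. Parent arm is known and a split could be produced later. Protocol 4.2 reports similar lung-function and biomarker effects at 200 mg and 300 mg q2w in DRI12544, and says dupilumab was generally well tolerated. All of this stands, and it limits the point to presentation, mainly of PK. It does not remove it: Protocol 4.2 says nothing about concentrations or ADA at the two q2w doses, and the Week 0 mixture follows directly from the definition.

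A reader might infer more, in four ways that the documents do not support.

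- *That every Dupilumab/Dupilumab column is affected, or that unbroken 300 mg q2w appears nowhere.* Results are shown by parent study, and the EFC13691 and PDY14192 columns are purely continued 300 mg q2w.
- *That the DRI12544 rise is also a dose artefact.* Those patients had at least 16 weeks off drug, Week 0 set to zero and a loading dose. A split by arm there would not isolate unbroken treatment.
- *That a safety signal is being hidden.* Protocol 10.6.2 mentions more local injection-site reactions at 300 mg weekly, which is a reason to look by dose history. No figure in the documents shows a consequence of moving from 200 mg to 300 mg q2w.
- *That SAP version 3 removed a dose split.* The categories dropped in SAP 1.6 (naïve, re-treated, interrupted, continuously treated) describe continuity by name, not dose. The reason given, between-study variation, simply does not bear on a split within one study.

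**Conclusion.** The point holds for the EFC13579 Dupilumab/Dupilumab column. Its Week 0 concentrations combine two dose levels in about equal numbers. The mean would then rise about 20% (dose-proportional trough) to 31% (upper bound inferred from Protocol 4.2) through the dose change alone. About 634 of about 760 patients on unbroken 300 mg q2w have no column of their own.

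The counts assume full rollover. The percentages assume equal rollover by arm, former 300 mg patients at steady state at Week 0, and later values at the 300 mg steady state. The 200-to-300 mg concentration ratio is inferred, not reported. No primary-endpoint estimate is wrong, and the choice of dose is not in question. This is an inexpensive improvement that lets systemic exposure be read correctly in the largest parent study.

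**What to change.** In SAP 2.3.2, split the EFC13579 Dupilumab/Dupilumab column by actual parent regimen (200 mg q2w, 300 mg q2w) for Week 0 and by-visit PK, ADA, and the TEAE, SAE and AESI overview tables. Keep the pooled column as a total. Say the same in SAP 2.4.6.1, which already sets Week 0 rules by parent study and by placebo or dupilumab history. The other parent studies need no change on this point.

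The cost is extra columns, each about half the size of the pooled one, so percentages are less precise. No new data are needed.

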2.3.3 Efficacy populations

The efficacy analysis population is the same as the safety population.

2.3.4 Pharmacokinetics (PK) population

The PK population will consist of all the patients in the safety population who had at least one non-missing functional dupilumab concentration value after the 1st dose of study drug in the current study.

2.3.5 Anti-drug antibody (ADA) population

ADA Population will consist of all the patients in the safety population who had at least one nonmissing ADA result in the ADA assay after the 1st dose of study drug in the current study.

2.4 STATISTICAL METHODS

2.4.1 Demographics and baseline characteristics

The demographics and baseline characteristics will be summarized for the safety population. The data for demographics and baseline characteristics will be obtained from the original baselines of the parent studies. Continuous data will be summarized by the treatment category and overall (see Section 2.3.2), using the number of available data, mean, standard deviation (SD), median, minimum, and maximum. Categorical and ordinal data will be summarized by the treatment category and overall (see Section 2.3.2), using the number of 2.3.2), using the number of available data will be summarized by the treatment category and overall (see Section 2.3.2), using the number of 2.3.2), using the number and percentage of patients.

Parameters described in Section 2.1.1 will be summarized for the safety population by the treatment category and overall (see Section 2.3.2) using descriptive statistics.

Medical and surgical history will be summarized by the treatment category and overall (see Section 2.3.2), by system organ class (SOC) and preferred term (PT) sorted by internationally agreed order of SOC and by the decreasing frequency of PT within SOC based on the overall group. Comorbidity history and atopic medical history will be summarized separately.

No specific description of the safety/efficacy parameters will be provided at baseline. If relevant, the baseline values will be described along with each safety/efficacy analysis.

2.4.2 Prior or concomitant medications

The prior medications, concomitant medications in parent study, and concomitant medications will be presented for the safety population by the treatment category and overall (see Section 2.3.2). The prior medications are those the patients used prior to the first IMP dose in the parent study. The data of prior medications are obtained from the parent study. Medications will be summarized according to the WHO-DD dictionary, considering the first digit of the ATC class (anatomic category) and the first 3 digits of the ATC class (therapeutic category). All ATC codes corresponding to a medication will be summarized. Patients will be counted once in each ATC category (anatomic or therapeutic) linked to the medication, and therefore patients may be counted several times for the same medication.

The table for prior medications will be sorted by decreasing frequency of ATC followed by all other therapeutic classes based on the overall incidence. In case of equal frequency regarding ATC (anatomic or therapeutic), alphabetical order will be used.

The tables for concomitant medications in parent study will be sorted by decreasing frequency of ATC followed by all other therapeutic classes based on the overall incidence. In case of equal frequency regarding ATCs (anatomic or therapeutic categories), alphabetical order will be used.

The tables for concomitant medications will be sorted by decreasing frequency of ATC followed by all other therapeutic classes based on the overall incidence. In case of equal frequency regarding ATCs (anatomic or therapeutic categories), alphabetical order will be used.

In addition, the ICS in combination with allowable controller medication(s), the salbutamol/albuterol or levosalbutamol/levalbuterol reliever medication, and the OCS medication (for patients from EFC13691 only) will be summarized separately.

2.4.2.1 ICS in combination with allowable controller medication(s)

ICS in combination with allowable controller medications and the OCS medication (for patients from EFC13691 only) taken within 30 days prior to screening of parent study will be summarized by the treatment category and overall (see Section 2.3.2), and will be sorted by decreasing frequency of medication name in the overall category. The data of prior ICS and controller medications and the OCS medication (for patients from EFC13691 only) are sourced from the parent studies.

The prescription of ICS in combination with allowable controller medication(s) at enrollment of LTS12551 will be summarized by the treatment category and overall (see Section 2.3.2). Number (%) of patients will be presented by medication names and also by ICS dose level (medium/high as defined in Appendix C) according to the classification specified in (9). The descriptive summary for the percentage change from baseline in OCS dose will be presented in the efficacy evaluations for patients from EFC13691.

2.4.2.1.1 Compliance for ICS and controller medications

During the LTS12551 study, the prescription of background asthma controller medications is reported on the eCRF, and the daily intake is recorded on the electronic diary by patients. The use of electronic diary will be stopped after the approval of protocol amendment 4 in LTS12551. The compliance for the controller medications with ICS component will be calculated for each patient, based on the data observed up to the end of electronic diary collection.

For a patient from DRI12544 study, a morning/evening dairy is compliant if the number of puffs administered is the same as or greater than what is prescribed. **Percentage of Compliance** is defined as the total number of controller medication puffs taken divided by the total number of expected puffs of controller medication during the treatment period (ie, from the evening dairy of the first IMP dose date in LTS12551 study to the morning dairy of the last IMP dose in LTS12551 study + 14 days). The total number of controller medication puff taken is the sum of the controller medication puffs captured in each morning and evening diary during the treatment period, with each diary being capped at the number of puffs expected per diary, according to the patient's prescribed controller medication dosing regimen.

For a patient from EFC13579, EFC13691 or PDY14192 studies, due to changes in the design of electronic diary logpad, the daily intake of each prescribed asthma controller medication is recorded on the electronic diary every evening. An evening diary is considered as compliant to the prescribed controller medication with ICS component if the actual dose of each controller medication with ICS component is same as or greater than the prescribed dose. **Percentage of Compliance** is defined as the number of days when the patient is compliant to the prescribed controller medication(s) with ICS component divided by the number of days the patient stays in the treatment period (from first dose to last dose + 14 days).

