9.2.2.7 Disease-specific, daily efficacy assessments

All the data detailed in this section will no longer be collected for all patients upon approval of Amendment 04.

Prior to Amendment 04, on a daily basis throughout the study, the patient used an electronic diary / PEF meter to:

- Measure morning and evening PEF;
- Respond to the morning and evening asthma symptom scale questions;
- Indicate the number of inhalations/day of salbutamol/albuterol or levosalbutamol/levalbuterol for symptom relief;
- Record the number of inhalations/day of background ICS and controller therapies used.

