1.6 STATISTICAL MODIFICATIONS MADE IN THE STATISTICAL ANALYSIS PLAN

This statistical analysis plan (SAP) version 3.0 is based on the LTS12551 amended protocol 2 (protocol amendment 4) dated October 31st, 2016, and is the third version of SAP for LTS12551.

SAP version number	Date approved	Rationale	Description of statistical changes
2	23-Nov-2016	Protocol amendment 4 shortens the open-label treatment period to 48 weeks.	The open-label treatment duration is amended to 48 weeks for patients providing consents after the implementation of the protocol amendment 4.
2	23-Nov-2016	Protocol amendment 4 drops the electronic diary, PEF meter, EQ-5D-3L, serum immunoglobulins, and serum total IgE for all the patients in LTS12551 study. Before the protocol amendment 4 becomes effective, the patients from	The analyses for AM/PM PEF, AM/PM asthma symptom score, number of reliever uses, number of nocturnal awakenings, EQ-5D-3L score, serum immunoglobulins and serum total IgE in LTS12551 study will be restricted to the patients from the DRI12544 study and performed to the data observed up

SAP			
version	Date		
number	approved	Rationale	Description of statistical changes
		DRI12544 study have data collection for the aforementioned endpoints for more than one year, while only a few of patients from EFC13579, EFC13691 or PDY14192 studies have limited amount of data collected for those endpoints.	to the end of their collection. The compliance for background controller medications will be calculated using the data observed up to the end of the electronic diary collection.
2	23-Nov-2016	Protocol amendment 4 adds three efficacy endpoints linked to the prescribed OCS dose for the patients from the EFC13691 study only. They are the percentage change from baseline in the OCS dose, the proportion of patients achieving a reduction of 50% or greater in the OCS dose compared with the baseline, and the proportion of patients whose background OCS are completely tapered off. The baseline OCS dose is defined as the original baseline value of the parent study.	The proportion of patients whose background OCS are completely tapered off and its analysis have been added to this version of SAP, and the other two endpoints linked to the OCS dose and their corresponding analyses have already existed in the SAP 1.0.

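### The printed formulas for background-controller compliance run to last dose + 14 days although the e-diary behind them stops at Amendment 04, which contradicts the SAP's own data cut-off

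*SAP*

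**What the plan says.** SAP 2.4.2.1.1 opens by saying that compliance with ICS-containing controllers is calculated for each patient, "based on the data observed up to the end of electronic diary collection". SAP 1.6 repeats this limit. The section then gives two definitions.

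- **DRI12544:** "the total number of controller medication puffs taken divided by the total number of expected puffs of controller medication during the treatment period". The period is spelled out as running to the morning diary at last IMP dose + 14 days. The numerator is the "sum of the controller medication puffs captured in each morning and evening diary during the treatment period", with each diary capped at the puffs expected.
- **EFC13579, EFC13691, PDY14192:** "the daily intake of each prescribed asthma controller medication is recorded on the electronic diary every evening". Compliance is the number of days on which every ICS-containing controller was taken at or above the prescribed dose, with the ICS "component divided by the number of days the patient stays in the treatment period (from first dose to last dose + 14 days".

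Protocol 9.2.2.7 lists controller intake among the daily diary items and says: "All the data detailed in this section will no longer be collected for all patients upon approval of Amendment 04". Footnote g to Protocol 1.3 confirms that the diary is not used for patients enrolled after Amendment 04. On how much diary data exist for the other daily endpoints, SAP 1.6 says that DRI12544 patients have more than one year, while "only a few of patients from EFC13579, EFC13691 or PDY14192 studies have limited amount of data collected".

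**The concern.** The numerator can grow only while the diary is running. The denominator, as printed, keeps growing until treatment ends. For a patient treated beyond diary stop, the ratio then mixes adherence with the share of treatment time that the diary happened to cover.

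The population is open as well. SAP 2.1.3.6 restricts the four daily efficacy endpoints to DRI12544. Controller compliance has no such restriction: it is for each patient, and the other three parent studies get their own formula. No rule covers patients who never had a diary in this study.

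There is also a difference of scale. The DRI12544 percentage gives partial credit for each puff; the other formula counts a day as compliant or not. SAP 2.3.2 asks for each planned analysis in non-OCS patients by parent study and for *All*, so the combined column would mix the two.

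Dupilumab is given on top of maintained ICS and controller therapy. A table showing poor or uneven adherence that merely reflects the amendment date would mislead readers about that background.

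**Working it through.** The documents state no compliance figure, so there is none to reproduce. The check applies the printed formulas to a patient of known adherence.

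**Inputs**

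- Treatment length: 48 or 96 weeks (Protocol 6.2.1). The EOT visit is 2 weeks after the last dose (Protocol 10.1.1.16, 10.1.2.12), so first dose to last dose + 14 days is 46 × 7 + 14 = 336 days or 94 × 7 + 14 = 672 days.
- Diary weeks *d* in this study: **assumed**, because the documents give no individual stop dates. A range is shown.
- True adherence *c* while the diary was running: 1.0 unless stated.

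**Formulas**

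- Printed: 100 × *c* × 7*d* / (treatment days).
- Cut at diary stop: 100 × *c* × 7*d* / 7*d* = 100 × *c* for *d* > 0, and 0/0 (not evaluable) for *d* = 0.

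**Fully adherent patient treated for the planned period**

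| Planned weeks | Diary weeks *d* (assumed) | Printed formula | Cut at diary stop |
|---|---|---|---|
| 96 | 8 | 56/672 = 8.3% | 100% |
| 96 | 24 | 168/672 = 25.0% | 100% |
| 96 | 52 | 364/672 = 54.2% | 100% |
| 96 | 72 | 504/672 = 75.0% | 100% |
| 96 | 84 | 588/672 = 87.5% | 100% |
| 96 | 96 | 672/672 = 100% | 100% |
| 48 | 0 (enrolled after Amendment 04) | 0/336 = 0% | not evaluable |

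The puff version behaves the same way. At an assumed 4 puffs a day and 52 diary weeks, it gives 4 × 364 = 1,456 of 4 × 672 = 2,688, or 54.2%. With *c* = 0.9 and 52 diary weeks, the printed formula gives 0.9 × 364/672 = 48.8% against 90%.

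As a yardstick, SAP 2.4.3.2 flags IMP compliance below 80%. On the printed controller formula, a perfect 96-week patient needs 0.8 × 96 = 76.8 diary weeks to reach that level.

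**Scale.** Suppose a patient takes 3 of 4 prescribed puffs of an ICS-containing controller every day, with complete diaries throughout. The DRI12544 formula gives 3/4 = 75%. The day-based formula gives 0%, because no day meets the prescribed dose. This gap does not depend on where the denominator stops.

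**The case against.** The best defence is the opening sentence of the section, repeated in SAP 1.6. It can fairly be read as governing the whole calculation, denominator included. On that reading nothing is understated, and patients without a diary simply have no observed period. This stands to the extent that a reader who infers that understatement is built into the plan goes too far. The SAP contains a rule and two formulas that conflict, and it does not say which prevails. Likewise, a reader might infer that the plan assigns 0% to patients without a diary. That is only the literal result of the formula; the SAP prescribes neither 0% nor exclusion.

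The defence does not remove the problem. The sentence limits observed data, whereas the denominators are built from dosing dates and expected puffs, which are not diary observations. Where the SAP wants a calculation cut at diary stop, it can say so: SAP 2.5.2 does this for the periodic averages of the daily endpoints. The missing-data exclusion in SAP 2.5.3 covers categorical variables and does not settle the case.

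A reader might also take this as the only evidence on background therapy. It is not. SAP 2.1.2 has all medications taken during the study reported on the CRF, and SAP 2.4.2 summarises them. The diary is the only source that the SAP names for daily intake counts.

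The SAP explains the two definitions by a change in diary design, presents results by parent study as well as *All*, and analyses EFC13691 separately. The 75% against 0% example is deliberately extreme. Those points limit the harm, but they give no meaning to a combined DRI12544, EFC13579 and PDY14192 percentage.

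**Conclusion.** Wrong as written, minor severity. The printed denominators contradict the section's own data limit. Applied literally, they understate compliance for patients with some recorded adherence who stayed on treatment after diary stop. Patients who finished or stopped treatment earlier are unaffected.

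The size depends on unknown diary durations. For a fully adherent 96-week patient it ranges from 8% at 8 diary weeks through 54% at 52 to no loss at 96. None of these should be read as typical: SAP 1.6 indicates only more than a year for DRI12544 and limited data for a few others. The scale mismatch in the non-OCS *All* column holds on either reading.

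The consequence is confined to a descriptive background-therapy table. The TEAE primary endpoint, injection-based IMP compliance (SAP 2.4.3.2), the analysis populations and the efficacy summaries do not use this measure.

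**What to change.** In SAP 2.4.2.1.1:

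1. End both numerator and denominator, in both formulas, at the earlier of last IMP dose + 14 days and the patient's last date of e-diary collection.
2. Calculate compliance only for patients with at least one diary day in LTS12551. Report the number not evaluable by parent study, and state that absence of a diary is not scored as non-compliance.
3. Show the puff-weighted DRI12544 percentage separately from the day-based percentage of EFC13579 and PDY14192, with no combined figure in the non-OCS *All* column.

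The cost is a few sentences of SAP text and one date cap in the derivation. The downside is that fewer patients contribute to the table, and the result describes adherence only while the diary was in use; a footnote should say so.
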